Patients determined to be eligible for the study by the patient's clinical provider (and per our previously defined criteria) will be recruited to enroll in the project within the first 24 hours of their hospital admission (i.e. 24 hours following the documented H&P Note). They will be offered the opportunity to consent to enrollment in the study and will be assigned by the study team into either the intervention (RibFx belt +current standard of care) (n=35 subjects) or control (current standard of care) arm (n=15 subjects) in a quasi-experimental prospective design: untreated control group with dependent pretest and posttest samples. In this manner, the intervention arm will be both compared to themselves (pretest vs. posttests) as well as to a control group not exposed to the intervention.

Patients upon enrollment in the study will undergo an initial assessment that will include their baseline pain scores, narcotic

consumption, incentive spirometry scores, and the subjective self-reported results of their questionnaire (the pre-test questionnaire- see attached). Patients will continue to be scored on objective (incentive spirometry results, opioid pain medicine consumption) and subjective variables (pain scores) during their hospital course. Between 24-48 hours after enrollment, they will be prompted to again complete a similar 2nd questionnaire post-test (if they are discharged from the hospital at this point in the time course, they will be sent home with the questionnaire and prompted to complete it at home, or asked for an agreed upon time and day for study staff to call the patient to complete the questionnaire over the phone). At their follow up appointment in trauma clinic (which will be coordinated by the research team to be as close as possible to 3 weeks post injury), they will have the opportunity to again voluntarily complete a final short questionnaires (post-test) that assess their pain control and respiratory function over the last 3 weeks. If the patient does not plan to follow up in trauma clinic (or is not asked to), we will ask the patient for an agreeable time and day to call the patient and administer the questionnaire over the phone. At this point, their involvement in the trial will be complete.

All aspects of data collection will be performed only by approved members of Key Personnel.

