Patients themselves will play an active role in data collection during the trial, and will be instructed and prompted in how to do so. One key change from the prior iteration of the protocol was that before, UVM staff nurses would collect research data while the patient was inpatient. Because they are not research personnel, we will no longer ask them to do so. Patients will be expected to fill out a worksheet on a daily basis, both while inpatient and after discharge, on their daily incentive spirometry scores as well as their minimum and maximum pain scale scores. This will be used to supplement the survey or questionnaire data, as well as the objective data from the EMR.

We will ultimately compare groups using a quasi-experimental design as follows: Untreated control group with dependent pretest and posttest samples. This will allow for a direct comparison of patient to patient within the intervention arm (patient pretest result serving as control compared to posttest result) (n=35 patients). To observe for temporal variability, we will have a control group with no intervention as well (no rib belt worn) (n=15), however the principle aim of the study is the comparison of patients to themselves in a pre-test, post-test fashion.

PURPOSE AND OBJECTIVES

Purpose: *The importance of the research and the potential knowledge to be gained should be explained in detail. Give background information.*

The purpose of this study is to ascertain whether the use of next generation rib orthosis belts (such as the RibFx) can improve patient outcomes following traumatic rib fractures within our population, whether it be by improving pain control, decreased respiratory complications, or increased patient satisfaction. We hypothesize that the use of elastic rib belts will improve rib fracture pain control without compromising pulmonary function (statistically significant improvement in pain control without significant impairment in respiratory function or increase in respiratory complication). We feel as though answering this question can help us as providers to improve the quality of care to our patients in our department.

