All patients will undergo initial "Pre-test" testing which will include baseline pain scores (1-10 traditional pain scale), initial narcotic consumption (in MME) for first 24 hours of hospitalization, maximum incentive spirometry score for first 24 hours of hospitalization, and pre-test questionnaire result (see attached questionnaire #1). As the study continues their relevant data will be collected, including both objective (incentive spirometry scores, opioid pain medication consumption, incidence of atelectasis and pneumonia) and subjective (pain scores, survey result) clinical data. Concurrently, we will complete the trial with the intervention (RibFx belt) phase in which participants will be enrolled in the interventional arm of the study. The objective and subjective data will be collected in an identical fashion- the only difference between groups will be that this group will have been fitted with the RibFx belt for their hospital course and discharge.

The participants (both in the control and interventional groups) will again be asked to complete essentially the same brief surveys in a post-test fashion at two set time points: between 24-48 hours after initial enrollment in the study (Questionnaire #2)(if patient has been discharged at this point, they will be sent home with this survey and instructed when to complete, or facilitated completion by calling the patient at this time), and at 3 weeks post-injury (this will be done at their clinic visit, assuming they are not still admitted to the hospital at this time point).

Patients will also be sent home with a work-book to record their incentive spirometry scores and pain scores (all patients will be sent home with an incentive spirometer, and all patients in the interventional group will be sent home with their Ribfx belt).

[figure not shown]

The following schematic will be used for enrollment group assignment in the study (n=50 total participants):

During the chart review portion of the study, patients who have authorized to have their medical records reviewed will have their post-traumatic records reviewed for the following diagnoses or conditions: respiratory failure, tracheostomy requirement, pneumonia, tube thoracostomy (chest tube), epidural use, intubation rates, hospital length of stay, and mortality.

[figure not shown]
The following schematic represents the patient/subject trial course:

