Each patient in the interventional arm will be fitted with a RibFx orthosis belt, which is to be worn during the majority of their day (excluding showering/bathing). It will be encouraged (though not mandatory) to wear at night. Patients in both the control and interventional arm will be expected to participate in pulmonary hygiene / toilet exercises with guided and independent incentive spirometry as per our normal routine and standard of care. There are no other interventions or procedures that the patients will be subjected to for the research trial- other procedures/interventions will be performed only if the clinical care team feels they are indicated.

For research involving survey, questionnaires, etc.: *Describe the setting and the mode of administering the instrument and the provisions for maintaining privacy and confidentiality. Include the duration, intervals of administration, and overall length of participation. (describe and attach all instruments)*

Not applicable

Patients will be assessed with three short questionnaires in a pretest , posttest fashion at both the onset of the study, 24-48 hours after enrollment, and at their follow-up appointment 3 weeks after (2 post test questionnaires). The initial evaluation will occur on initial assessment prior to placement of the rib belt (or, for the control/ non-intervention group, at the onset/first 24 hours of the study).

Each of the questionnaires is essentially the same with only brief modifications made in the first two questions to make them appropriate for the timing during the clinical course. However these are all attached (see Questionnaire 1,2, and 3). Questionnaires 2 and 3 may be facilitated over the phone if the patient is discharged before the defined time frames are met.

Patients in both the intervention and control arms will present in post-admission follow up at a time period of 3 weeks post injury (range, 2-4 weeks) following their hospital admission, and will be asked to fill out a brief survey regarding their respiratory function and pain control. This survey will also inquire into compliance with the use of incentive spirometer, and compliance with the use of the RibFx belt (for patients in the intervention arm). If patients are not asked to present to trauma clinic for follow up, or if a patient does not intend to follow up, we will aim to complete this questionnaire over the phone in the same time frame.

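### Any pain or breathing item in the final questionnaire that looks back over 3 weeks is not comparable with a first-day pre-test, and the protocol does not say which items do

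*Combined protocol and SAP*

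**What the plan says.** The study is built on within-patient change. The data-collection and design text before Purpose and Objectives states that "the principle aim of the study is the comparison of patients to themselves in a pre-test, post-test fashion".

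- **Pre-test.** Patients "will be recruited to enroll in the project within the first 24 hours of their hospital admission". The section on surveys and questionnaires under Procedures adds: "The initial evaluation will occur on initial assessment prior to placement of the rib belt". Under Study Design, the matching baseline opioid measure is "initial narcotic consumption (in MME) for first 24 hours of hospitalization".
- **Final post-test, timing.** Patients are seen "at a time period of 3 weeks post injury (range, 2-4 weeks"), or telephoned in the same period.
- **Final post-test, content.** The opening study summary calls it a "post-test) that assess their pain control and respiratory function over the last 3 weeks". The questionnaire section describes the same survey as covering breathing and pain, with no look-back period.
- **Wording across the three forms.** The questionnaire section says they are "essentially the same with only brief modifications made in the first two questions to make them appropriate for the timing during the clinical course".

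Questionnaires 1 to 3 are attachments and are not in the text available. Statistical Considerations says that pre-test and post-test answers will be compared. It gives no recall period for any item and does not define the 3-week change. Separately, patients keep a daily worksheet of lowest and highest pain and of spirometry, in hospital and after discharge, as a supplement to the questionnaires.

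**The concern.** A change score means change only if both measurements ask about the same length of time. On the opening summary's wording, the pre-test reports about one day and the final post-test reports a remembered summary of the recovery. Part of the difference between them then comes from the question, not the patient.

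The one-group comparison carries the study's main aim, so nothing cancels this artefact there. The control group has the same questionnaires, but Statistical Considerations says the study is not powered to compare the arms. What is at stake is whether the 3-week questionnaire result can be read as the patient's state after three weeks of belt use.

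**Working it through.** **The plan's own figure.** Statistical Considerations gives 83% power at n = 30 and 88% at n = 35 for a 20% fall in MPQ PRI (mean 28, SD 16, within-subject correlation 0.8, two-sided 0.05).

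- Target change: 0.20 × 28 = 5.6.
- SD of change: 16 × √(2 × (1 − 0.8)) = 10.12.
- Paired t-test power: 83.4% at n = 30 and 88.9% at n = 35.

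The stated figures reproduce and are not in dispute.

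**What a 3-week window covers.** Days are counted from injury, and the visit range is 2 to 4 weeks.

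- Visit at day 14: the window reaches back 21 − 14 = 7 days before the injury.
- Visit at day 21: it starts at the injury. The pre-test day is about 1/21, or 5%, of it.
- Visit at day 28: it starts at 28 − 21 = day 7 and leaves out the pre-test day.

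One item would therefore summarise different phases of recovery depending on the visit date.

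**What averaging does to a falling pain course.** Two assumptions are needed that the documents do not give: the patient reports the plain average over the window since injury, and pain follows a given curve. Let T be the visit day and a = max(0, T − 21) the start of the window.

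- Linear decline: share of the true fall shown = ((a + T)/2)/T. At day 21 this is 10.5/21 = 50%; at day 14, 7/14 = 50%; at day 28, 17.5/28 = 63%.
- Exponential decline towards zero with time constant τ: true fall = 1 − exp(−T/τ); fall shown = 1 − τ[exp(−a/τ) − exp(−T/τ)]/(T − a).

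Share of the true fall that the window average shows:

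| Assumed curve | Day 14 | Day 21 | Day 28 |
|---|---|---|---|
| Linear | 50% | 50% | 63% |
| Exponential, τ = 14 days | 58% | 62% | 79% |
| Exponential, τ = 7 days | 66% | 72% | 90% |
| Exponential, τ = 3 days | 80% | 86% | 99% |

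In percentage points at day 21, with k = ln 2 / half-life, true fall = 1 − exp(−21k) and fall shown = 1 − (1 − exp(−21k))/(21k):

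| Assumed half-life | True fall | Fall shown | Gap |
|---|---|---|---|
| 7 days | 87.5% | 57.9% | 30 points |
| 10 days | 76.7% | 47.3% | 29 points |
| 14 days | 64.6% | 37.8% | 27 points |

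All of these are illustrations of direction and possible size, not estimates for this trial.

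**The case against.** The strongest reply is that no questionnaire item can be seen. The 3-week period appears once, in a descriptive sentence, while the more detailed questionnaire section confines timing changes to the first two questions. Items worded identically at all three time points do not have this mismatch. This stands: a reader might infer that the whole final score is a 3-week average, and the documents do not support that. It does not remove the point. Either some pain or breathing items carry the long window and are not comparable with the pre-test, or none do and the opening summary misdescribes the form.

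Three other tempting readings also go too far.

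- *The final window always contains the pre-test.* It does not at day 28, and at day 21 the pre-test day is only about 5% of it. The main issue is averaging over the recovery, not the overlap.
- *Pain at 3 weeks will be unknown.* The daily worksheet can supply it, and Questionnaire 2, at 24 to 48 hours, is not touched by this wording. The worksheet has its limits: it is described as supplementary and records no breathing symptoms.
- *The study loses its power.* The understated falls above, 38% to 58%, still exceed the 20% target. That target is also for MPQ PRI, whereas the questionnaires are said to draw on the CAT and BPI, so it is not a benchmark for them.

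It may also be said that pain over the whole period of belt use is a legitimate quantity, and that understating improvement is conservative. Both are fair for pain. But the period average is a different quantity from change since the pre-test, and the same averaging would understate a gradual worsening of breathing, which is not conservative for a claim of no respiratory harm.

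**Conclusion.** The point holds in a limited form. The protocol gives two descriptions of the final questionnaire that do not sit together. For any pain or breathing item with the 3-week window, pre-post change is confounded with a change of recall period, and the period covered shifts with the visit date.

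For a falling pain course the direction is an understatement of the change to 3 weeks. Its size cannot be fixed from the documents. At day 21 the assumed curves show between 50% (linear) and 86% of the true fall, and half-lives of 7 to 14 days give a gap of 27 to 30 percentage points. These figures assume that recall is a plain average and, for the exponential curves, that pain decays towards zero.

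How many items are affected is unknown without the attachments. The finding does not reach Questionnaire 2, the daily pain record or the stated power calculation.

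**What to change.** 1. Reconcile the opening study summary with the questionnaire section, and state the recall period of every item.
2. Use one identical short recall window, for example the past 24 hours, for all pain and breathing severity items in Questionnaires 1, 2 and 3.
3. In Statistical Considerations, define pre-post change on those items only.
4. Keep 3-week recall for the compliance and medication-use questions, where it fits the purpose.
5. Use the daily worksheet for pain across the 3 weeks.

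The cost is rewording with IRB notice; no data collection is added. The small loss is a single remembered 3-week summary, which the worksheet replaces for pain. The change has to precede completion of the forms, since a recall period cannot be altered once answers are given.

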In this study, we will utilize a quasi-experimental design to compare 35 subjects to themselves in a pre-test, post-test fashion. In addition, we will have an additional 15 non-interventional control patients to observe for temporal changes in patient's symptoms not secondary to the intervention itself. However, it is important to note that the study is not powered to detect differences between the control group and the intervention group. The purpose of the control group is to observe for differences that occur in this population over time regardless of intervention (it should be assumed that pain will improve as time increases from the set injury point, regardless of intervention). Further, this preliminary data could potentially be used to calculate an accurate power calculation for a definitive randomized controlled trial.

Groups will be compared by demographical and clinical data to determine what potentially confounding differences exist between the arms of the study. Relevant objective data that will be used to determine group differences include (but not limited to): age, sex, tobacco use status (active/former/none), presence of asthma, presence of COPD, or presence of restrictive lung

disease, home oxygen use, obstructive sleep apnea/ CPAP use, chronic pain incidence, narcotic/opioid medication consumption, obesity/ BMI. We will also measure relevant variables of their clinical course such as regional block/anesthesia/epidural administration. Radiological appearance of presenting imaging (either CT Chest or chest X-ray) will be compared by a dedicated and blinded radiologist who will grade the initial imaging based on severity including the following variables: number of fractures, bilateral vs. unilateral, degree of displacement, presence of lung contusion, presence of pneumothorax, presence of intrinsic lung disease, pleural effusion or blood.

Survey results (both pretest and posttests) will be compared using the appropriate statistical methods depending on the questions construct: with Chi squared performed for categorical variables (such as multiple choice) and unpaired t test for continuous variables (such as likert scale rankings).

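### Daily pain and spirometry diaries are kept in both arms but have no stated analysis; a baseline-adjusted longitudinal model, labelled exploratory, should be prespecified

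*Combined protocol and SAP*

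**What the plan says.** The opening study description, just before Purpose and Objectives, sets up the diary: "Patients will be expected to fill out a worksheet on a daily basis, both while inpatient and after discharge, on their daily incentive spirometry scores", together with minimum and maximum pain. It then gives the diary's role: "This will be used to supplement the survey or questionnaire data, as well as the objective data from the EMR".

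Study Design does not limit the diary to one arm: "Patients will also be sent home with a work-book to record their incentive spirometry scores and pain scores". Of the two arms it says: "The objective and subjective data will be collected in an identical fashion". The Objectives name pain scores in the primary objective and spirometry scores in the secondary one.

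No end date is given for the diary. The last questionnaire is timed at "3 weeks post injury (range, 2-4 weeks) following their hospital admission", and the opening description says of that contact: "At this point, their involvement in the trial will be complete". A diary of about three weeks is therefore an inference.

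There is one pre-test and there are two post-tests, at 24-48 hours after enrolment and at 3 weeks. Statistical Considerations names tests for survey results only: chi-squared for categorical items and an unpaired t test for continuous ones. It gives no model, summary measure or missing-day rule for the daily series. It also says that "the study is not powered to detect differences between the control group and the intervention group". The principal aim is the pre/post comparison within the belt arm.

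**The concern.** Two variables named in the objectives are measured every day in both arms and have no stated analysis. The choice of day, of minimum or maximum pain, and of summary therefore stays open until the data are seen.

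The stated test also discards information. Applied between arms at a post-test, an unpaired t test ignores each patient's baseline and every diary day. Yet Statistical Considerations says the controls are there to show how patients change over time regardless of the belt, and the opening description says the belt arm will also be compared with them. A comparison of the two arms' courses over time, adjusted for baseline, answers that directly. It would also supply the variance and correlation estimates needed for the later randomized trial that the plan has in mind.

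**Working it through.** **Inputs.** From Statistical Considerations: MPQ PRI mean 28, SD 16, a 20% decrease, within-subject correlation 0.8, two-sided alpha 0.05. From Number of Subjects: 35 belt, 15 control. The effect is 0.20 × 28 = 5.6 points, or 5.6/16 = 0.35 SD. The documents give no SD or correlation for the daily pain scale or for spirometry, so applying these values to the diary is an assumption.

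**The plan's own figure.** Paired t test: SD of change = 16 × √(2 × (1 − 0.8)) = 10.12. Power is 83.4% at n = 30 (stated 83%) and 88.9% at n = 35 (stated 88%). It reproduces.

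**Between-arm power, equal correlation ρ.** Let f be the variance relative to one raw post-test.
- Raw mean of k days: f = (1 + (k − 1)ρ)/k
- Baseline-adjusted mean of k days: f = (1 + (k − 1)ρ)/k − ρ²
- Noncentrality = 0.35 / √(f × (1/35 + 1/15)), with √(1/35 + 1/15) = 0.3086; power from the noncentral t distribution.

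At ρ = 0.8:

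| Analysis | f | Noncentrality | Power |
|---|---|---|---|
| Raw single post-test (as planned) | 1.00 | 1.13 | 20% |
| Raw mean of 7 days | 0.829 | 1.25 | 23% |
| Adjusted single post-test | 1 − 0.64 = 0.36 | 1.89 | 46% |
| Adjusted mean of 2 post-tests | 0.90 − 0.64 = 0.26 | 2.22 | 59% |
| Adjusted mean of 7 days | 0.829 − 0.64 = 0.189 | 2.61 | 72% |

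With baseline adjustment on both sides, seven days cut the variance to 0.189/0.36 = 0.52 of the single post-test. Of the total fall from 1.00 to 0.189, adjustment alone accounts for 0.64.

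**Other correlations**, adjusted single post-test against adjusted 7-day mean: ρ = 0.3, 21% to 51%; ρ = 0.5, 25% to 50%; ρ = 0.9, 72% to 93%. Three recorded days give 65% at ρ = 0.8 and 41% at ρ = 0.5.

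**Decaying correlation.** Under AR(1) with lag-1 correlation r and baseline at day 0, f is the mean of r^|i−j| over the chosen days, minus the square of the mean of r^i. Days 2 and 21 stand in for the two questionnaires. Example, r = 0.8, days 2 and 21: (1 + 0.8¹⁹)/2 = 0.507; ((0.64 + 0.009)/2)² = 0.105; f = 0.402; power 42%.

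| r | Raw single (planned) | Adj. day 2 | Adj. day 21 | Adj. days 2 and 21 | Adj. days 1-7 | Adj. days 1-21 |
|---|---|---|---|---|---|---|
| 0.80 | 20% | 30% | 20% | 42% | 39% | 52% |
| 0.90 | 20% | 47% | 20% | 46% | 47% | 42% |
| 0.95 | 20% | 73% | 22% | 52% | 65% | 45% |

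The adjusted diary mean beats the planned raw test in every row. It also beats an adjusted day-21 value. It does not always beat an adjusted day-2 value or the adjusted mean of the two post-tests.

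All these figures assume complete diaries over the days used, equal variance on each day, and a belt effect that is constant from day 1.

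**The case against.** The strongest reply is that the plan disclaims this comparison. It is a pilot with a quality-improvement goal, its principal aim is within-arm, and the controls are there to show temporal change. The more serious weakness is the non-randomized sequence, whose final 25 patients all receive the belt. A mixed model leaves that confounding and any calendar trend in place, and calling its result the main between-arm estimate would give it too much authority. This stands, and it is why the analysis should be supportive and carry covariates.

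A reader might infer that the diary is shut out of every comparison, or that the trial rests on one post-test. The documents support neither. They leave the analysis of the diary unspecified rather than excluding it, and there are two post-tests.

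A reader might also infer that repeated measures by themselves would sharply improve precision. Without baseline adjustment, seven days raise power only from 20% to 23% at correlation 0.8. Against an adjusted early post-test, the gain vanishes or reverses once lag-1 correlation reaches 0.9-0.95.

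Two further points stand. A mean over days 1-7 is a different estimand from the 3-week value. Diary gaps may also depend on pain or belt intolerance, both of which Withdrawal Procedures lists as reasons for leaving, so missing at random is doubtful.

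None of this answers the core point: variables in the objectives have no stated analysis, and the stated test ignores the baseline.

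**Conclusion.** The point holds as a low-cost improvement to the analysis. On the plan's MPQ PRI inputs, a baseline-adjusted analysis of seven diary days has 72% between-arm power against 20% for the planned raw post-test at equal correlation 0.8, and 39-65% against 20% under AR(1) decay with lag-1 correlation 0.8-0.95. The fair comparison for the diary's own contribution is narrower: 46% to 72% against one adjusted post-test, or 59% to 72% against the adjusted mean of both, at equal correlation 0.8. Under decay, that contribution depends on the structure and the comparator, and it can be negative.

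The sizes are illustrative because the SD and correlation come from another instrument. A reader should not infer that the model separates the belt effect from natural recovery free of bias. Allocation is not randomized, so the arm contrast stays open to confounding. Nor should the diary be used to sharpen the within-arm comparison alone: the plan itself expects pain to fall without any intervention, and more precision there would only make that recovery easier to declare significant.

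**What to change.** Add to Statistical Considerations a prespecified, supportive between-arm analysis:

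- A linear mixed model for daily maximum pain, and a separate one for daily spirometry, with arm, day, arm-by-day and the pre-test value. Model within-patient correlation explicitly (for example random intercept and slope) and use all available diary days in both arms.
- A small number of the baseline confounders already to be collected under Study Design and Statistical Considerations, such as age, chronic pain and number of fractures. With 15 controls the list must be short and fixed in advance.
- The arm difference over a named window, for example days 1-7 and days 1-21, with a 95% confidence interval, labelled exploratory because allocation is not randomized and the comparison is not powered.
- A stated diary end date, and a sensitivity analysis for diary days that may not be missing at random.

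If the questionnaire items are also compared between arms, adjust them for the pre-test value; this needs no diary.

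The cost is a little more analysis work. No extra patients, visits or measurements are needed. The main downside is that self-kept diaries will be incomplete.
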